4 TRIAL DESIGN

4.1 Overall design

This is a Phase II, open-label, rollover trial to evaluate the safety and immunogenicity of one or two boost injections of Comirnaty or one dose of BNT162b2s01 in BNT162-01 trial subjects or two boosting doses of Comirnaty in BNT162-04 trial subjects. There will be two groups.

 Group A*: Trial subjects from BNT162-01 who received two injections of 30 µg Comirnaty will be randomized 2:1 to one booster injection (BNT162b2s01:Comirnaty). Day 1 (baseline in this trial) must occur ≥24 weeks after the last Comirnaty injection in the BNT162-01 trial.
Clinical Trial Protocol BNT162-14 Page 37 of 91 Version: 4.0 Date: 20 JAN 2022

 Group B: Trial subjects in either the trial BNT162-01 or BNT162-04 who did not receive the full two vaccinations of 30 µg Comirnaty will be offered two injections of 30 µg Comirnaty as per the conditional marketing authorization. Day 1 (baseline in this trial) must occur ≥12 weeks after receiving the last BNT162 candidate vaccine in the BNT162-01 or BNT162-04 trial.

*Group A excludes transplant subjects from Cohort 13 of the BNT162-01 trial; consenting transplant subjects will enroll into Group B immunology subgroup and will receive one injection, which will be followed 3 to 7 months afterward by a second injection of Comirnaty. Henceforth this group is referred to as Group B transplants.

All potential rollover volunteers must enroll in this trial within less than 18 months of their last injection of a BNT162 candidate vaccine in the parent BNT162-01 or BNT162-04 trials.

BNT162-01 or BNT162-04 trial subjects, including trial subjects who are still in the followup phase of their parent trial, will be actively informed about this rollover trial once it has received all necessary regulatory and ethical approvals. Depending on the timing of followup in the parent trial, data from the parent trial may be used to determine eligibility in this rollover trial after the trial subject has consented. Once the trial subject has enrolled into this rollover trial, all safety reporting will occur through this rollover trial, this includes the reporting of AEs that are unresolved from the parent trial, SAEs, and clinical events of special interest (AESIs).

A Safety Review Committee (SRC) will be reviewing emerging safety data at least every 16 weeks until the last enrolled subject in Group A has completed 28 d of follow-up. The SRC may then decide to decrease the frequency of its cumulative safety data reviews to a minimum of once a year. The SRC will also review data from Group B (e.g., SUSARS) on an as needed basis but also specifically data emerging from the Group B transplant subjects.

For a summary of the trial as a flow diagram, see the Schema in Section 1.2. For the planned assessments and visits, see the Schedule of Activities (SoA) in Section 1.3.

This trial will enroll healthy volunteers aged ≥ 18 years who received one or two previous injections of a BNT162 candidate vaccine in either the BNT162-01 trial or the BNT162-04 trial. Volunteers will not be enrolled if they have received any COVID-19 vaccine outside of their parent trial.

The maximum number of trial subjects in the Group A (BNT162-01 trial subjects in Cohorts 1 to 14 who received 2 x Comirnaty 30 μ g) will be 90 and in Group B (all other BNT162-01 or BNT162-04 trial subjects) will be 459. A subset of Group B (n = 129) will be asked to participate in an immunologic subset evaluation.

Group A (previous 2 x Comirnaty 30 µg recipients from BNT162-01): n = 90

- BNT162-01 trial Cohorts 2 and 10: n = 24
- BNT162-01 trial Cohort 12: n = 31 (of 90)
- BNT162-01 trial Cohort 13: n = 15 HIV-infected subjects
- BNT162-01 trial Cohort 14: n = 20

BioNTech SE	Clinical Trial Protocol	Page 38 of 91 Version: 4.0
Confidential	DINT 102-14	Date: 20 JAN 2022

The immunology subset of Group B (BNT162-01 or BNT162-04 trial subjects who did not receive 2 x Comirnaty 30 μ g and Cohort 13 transplant patients) whom will be asked to participate in reactogenicity and detailed immunologic assessments: n = 129

- BNT162-01 trial BNT162b1 Cohorts 2, 5 and 1: n = 36 (of 120)
- BNT162-01 trial BNT 162b2 Cohort 11: n = 30
- BNT162-01 trial BNT 162b2 Cohort 13: n = 15 transplant subjects
- BNT162-04 trial BNT162b3 younger Cohorts 1, 2, 5, 7: n = 48 (of 96)

4.2 Scientific rationale for the trial design

The scientific rationale for this open-label trial is the following:

- to describe changes in vaccine-induced durability and T cell, B cell and antibody breadth to SARS-CoV-2 antigens before and after booster vaccines;
 - to assess if booster vaccines improve immune responses against variant B.1.351;
 - to describe changes in vaccine-induced correlates of protection (if identified from other BNT162 vaccine studies);
- to assess safety of additional BNT162 booster vaccines;
- to describe sequences of SARS-CoV-2 infections to increase understanding of the current SARS-CoV-2 strains in circulation and document if potential signs of immune pressure from vaccines, genetics, etc. on the virus are observed; and
- to assess changes in immune responses in transplant subjects with 3rd and 4th vaccinations.

4.3 Justification for dose

Trial subjects from the BNT162-01 and BNT162-04 trials who did not receive two injections with 30 µg Comirnaty will be offered the Comirnaty dose and injection schedule that received conditional marketing authorization. This is the same dose evaluated in the Phase III trial (BNT162-02/C4591001) and the dose for which the available pharmacovigilance data after Comirnaty administration to millions of individuals worldwide has confirmed a favorable safety profile with no specific safety concerns.

Trial subjects from the BNT162-01 trial who did receive two injections of 30 μ g Comirnaty will be offered a single 30 μ g Comirnaty or BNT162b2s01 booster injection. The safety and immunogenicity of the candidate vaccine BNT162b2s01 is not anticipated to be any different than for the prototype vaccine Comirnaty.

4.4 Trial completer and end of trial definitions

A trial subject is considered to have completed the trial if they have completed all planned visits as listed in the SoA (see Section 1.3).

The end of the trial is defined as the date of the last visit of the last subject in the trial.

5 TRIAL POPULATION

Investigators should always use good clinical judgment in considering a volunteer's overall fitness for trial participation. Some volunteers may not be appropriate for enrollment in the rollover trial even if they meet all inclusion/exclusion criteria.

5.1 Inclusion criteria

Volunteers are eligible for enrollment into this trial if all of the following criteria apply:

- 1. Have given informed consent by signing the informed consent form (ICF) before initiation of any trial-specific procedures.
- 2. Willing and able to comply with scheduled visits, treatment schedule, laboratory tests, lifestyle restrictions (including those requested by the German and federal Governments, e.g., to follow good practices to reduce chances of spreading COVID-19), and other requirements of the trial.
- 3. Have received BNT162 vaccine candidates in the BNT162-01 or BNT162-04 trials.
- 4. Remain overall healthy (i.e., has not medically deteriorated significantly since participation in the parent trial, is not anticipated to die in the next 26 weeks, and is able to provide blood as specified by the trial without anticipated, deleterious medical consequences) in the clinical judgment of the investigator based on medical history and physical examination. Screening clinical laboratory tests are to assess the subjects "new baseline" unless required for eligibility (e.g., platelets).

Note: In particular, caution should be used with a subject who has a history of cardiovascular disease, e.g., myocarditis, pericarditis, myocardial infarction, congestive heart failure, cardiomyopathy or clinically significant arrhythmia.

- 5. Agree not to enroll in another trial of an IMP, starting after Visit 0 and continuously until Visit 5 (Day 50).
- 6. Less than 18 months have passed since their last IMP injection in their parent trial.
- If they received 30 µg Comirnaty twice in the BNT162-01 trial, Visit 1 in this trial is ≥24 weeks after their last IMP injection, unless the subject is a Cohort 13 transplant subject of the BNT162-01 trial.
- If they received any other BNT162 vaccine candidate than Comirnaty in the BNT162-01 or BNT162-04 trial or are a Cohort 13 transplant subject, Visit 1 in this trial is ≥12 weeks after their last IMP injection.
- 9. Have not been diagnosed with SARS-CoV-2 infection in the 12 weeks prior to Day 1 (baseline). Subjects who screen-fail on this criterion may be rescreened.

Laboratory inclusion values

Hemogram/complete blood count (CBC): 10. Platelets = 125,000 to 550,000/mm³.

Clinical Trial Protocol BNT162-14 Page 40 of 91 Version: 4.0 Date: 20 JAN 2022

Chemistry:

11. Chemistry panel: the following apply: alkaline phosphatase (ALP), alanine aminotransferase (ALT), and aspartate aminotransferase (AST) are <3.0 times the upper limit of normal, and glomerular filtration rate (GFR) is ≥ 40 mL/min/1.73 m².

Note: Other collected chemistries per the SoA are considered "baseline" values should serious adverse events occur in this trial.

Immunocompromised subjects/BNT162-01 Cohort 13:

12. Immunocompromised subjects may be included if their clinical laboratory values are stable in the context of their disease, and if there is no acute deterioration present with the expected need to change their therapy within the 2 weeks after the anticipated trial vaccination.

Reproductive status

- 13. Women of childbearing potential (WOCBP) must test negative in a urine beta-human chorionic gonadotropin (β-HCG) test at Visits 0 and 1. Women that are postmenopausal or permanently sterilized will be considered as not having reproductive potential.
- 14. WOCBP must agree to practice a highly effective form of contraception during the trial, starting at screening and continuously until Visit 5 (Day 50). For guidance on what is considered a "highly effective form of contraception", see Section 10.4.2.
- 15. WOCBP must confirm that they practiced one highly effective form of contraception for the 14 d prior to screening.
- 16. WOCBP must agree not to donate eggs (ova, oocytes) for the purposes of assisted reproduction during the trial, starting after Visit 0 and continuously until Visit 5 (Day 50).
- 17. Men who are sexually active with a WOCBP and have not had a vasectomy must agree to use a highly effective form of contraception with their female partner of childbearing potential during the trial, starting after Visit 0 and continuously until Visit 5 (Day 50).
- 18. Men must be willing to refrain from sperm donation, starting after Visit 0 and continuously until Visit 5 (Day 50).

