- m If applicable, Visit 7 or Visit 6 should be used to inform Group B transplant subjects (Cohort 13 of the BNT162-01 trial) on Dose 2 and informed consent must be collected. If Visit 6 is applicable, then Visit 7 must be skipped. Thereafter the SoA in Table 2a is applicable.
- n Record any non-trial SARS-CoV-2 vaccinations that trial subjects receive during the trial in the CRF until the last trial visit.
- o If a transplant subject consents to receive a second vaccination (i.e., 4th dose since the parent trial), the SoA in Table 2a is then applicable, there will be no blood sampling for CMI testing at the visit of consent (Visit 6 or Visit 7).
- p Only for Group B transplant subjects: record any non-trial SARS-CoV-2 vaccinations that trial subjects receive in the CRF.

Abbreviations: AE = adverse event; AESI = adverse event of special interest; CMI = cell mediated immunity; CRF = case report form; d = day; ELISA = enzyme-linked immunosorbent assay; EOT = end of trial; h = hour(s); IMP = investigational medicinal product; inj. = (IMP) injection; NAAT = nucleic acid amplification-based test; NATAB = neutralizing antibody titers and antibody binding; SAE = serious adverse event; SRC = safety review committee; SARS-CoV-2 = the virus leading to COVID-19; SoA = schedule of activities; WOCBP = women of childbearing potential.

BioNTech SE	Clinical Trial Protocol	Page 15 of 91 Version: 4.0
Confidential	BN1162-14	Date: 20 JAN 2022

Table 2a: Schedule of events for Immunology Subgroup of Group B transplant subjects (injection 2)

Activity	Visit 8	Visit 9	Visit 10	Visit 11 ^g	Visit 12 ^g	Early termination
Week(s) (post-Dose 2)		1	4	12	26	
Day (post-Dose 2)	1	8+2	29±7	85±10	182±20	
	(3 to 7 months post inj. 1; pre-dose except inj. 2)	(~7 d post inj. 2)	(~28 d post inj. 2)	(~3 months post inj. 2)	(~6 months post inj. 2 EOT Visit)	
Collect informed consent						
Assess inclusion/exclusion criteria compliance						
Collect demographic and medical history						
Physical examination	X ^a	X ^a			X a	X a
Vital signs, body weight ^b	X c					
Urine pregnancy test for WOCBP	Х					Х
Blood draw for hematology testing (up to 3 mL) $^{\rm d}$	Х	Х	Х			
Allocation to IMP						
IMP injection, then observe subjects for ~1 h	Х					
Subject hotline availability	=>	=>	=>	=>	End	(End)
Oral swab for NAAT-based SARS-CoV-2 testing for surveillance	×	х	х	х	Х	×
Oral swab for SARS-CoV-2 sequencing ^e	Х	Х	х	Х	Х	Х
Blood draws for NATAB and nucleocapsid protein testing (15 mL)	×	х	х	х	х	x

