- Human reproductive safety data are limited for Comirnaty. Therefore, although human teratogenicity is not suspected based on the intended pharmacology of the compound, the use of one highly effective method of contraception is required in this trial (see Section 10.4). For further details, see in the current BNT162 IB.

RigNIToch SE	Clinical Trial Protocol	Page 34 of 91
		Version: 4.0
Connuential	DINT 102-14	Date: 20 JAN 2022

The risks and mitigations linked to the COVID-19 pandemic while participating in the trial include the following:

- The risk of becoming SARS-CoV-2 infected or unknowingly spreading the virus during participation in the trial; therefore, trial subjects will continue to be required to practice social distancing and infection prevention practices.
- Use of a Subject hotline for subjects to contact the trial site during their participation should they require guidance or experience symptoms suggestive of SARS-CoV-2 infection. If the subject reports symptoms of illness, e.g., enhanced respiratory disease or flu-like symptoms, the subject will be asked to return to the site for diagnostic measures. More specifically, respiratory disease or progression of flu-like symptomatology, such as non-resolution of the symptoms after 3 d, i.e., symptom kinetics that are inconsistent with SARS-CoV-2 RNA immunization, will trigger diagnostic measures, i.e., antigen and diagnostic nucleic acid SARS-CoV-2 testing with reflexive viral sequencing.

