6 TRIAL TREATMENTS

Trial treatment is defined as any investigational treatment(s), marketed product(s), intended to be administered to a trial subject according to the trial protocol.

IMP name:	BNT162b2 (Comirnaty) or BNT162b2s01.
Туре:	Vaccine (BNT162 RNA-LNP vaccine utilizing modRNA).
Administration route:	Intramuscular (IM); upper arm, musculus deltoideus. The same arm may be used for both immunizations. The non-dominant arm is preferred.
Dosing regimen:	Group A: One (at Day 1) IM injection with 30 µg of either Comirnaty or BNT162b2s01.
	Group B: Two (at Day 1 and Day 21) IM injections with 30 μg of Comirnaty, except Group B transplant subjects.
	Group B transplant subjects: Two IM injections of 30 µg of Comirnaty, with injection 2 administered 3 to 7 months after injection 1 (Day 1).
	The planned time points for injection of IMP for Groups A and B are provided in the SoA (Section 1.3).
Sourcing:	Provided centrally by the sponsor.
Packaging and labeling:	IMP will be provided in glass vials as open-label supply. Each vial will be labeled as required per country requirements. For details, see the Pharmacy Manual.

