6.5 Concomitant therapy

Trial subjects should not receive any live or live attenuated vaccination within 30 d before or after any trial injection e.g., measles, mumps, and rubella (MMR); oral polio vaccine (OPV); varicella; yellow fever unless medically indicated e.g., rabies.

Trial subjects should not receive any other vaccines within 14 d before or after any trial injection, e.g., influenza, tetanus, pneumococcal, hepatitis A or B. When possible standard or care vaccinations should be planned with the trial injections in mind.

Recording of concomitant therapy for Group A: any medication or vaccine (including overthe-counter or prescription medicines, vitamins, and/or herbal supplements, or other specific categories of interest), that the trial subject receives starting after Visit 0 until Visit 5, and any medications due to medical history started before Visit 0 must be recorded in the CRF along with the:

- Reason for use
- Dates of administration including start and end dates
- Dosage information including dose and frequency

Concomitant therapy recording is not required for Group B but will be recorded on the SAE or AESI report.

Any non-trial SARS-CoV-2 vaccine, that trial subjects receive starting after Visit 0 until the last trial visit (at the times listed in the SoA, Section 1.3) must be recorded in the CRF.

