10.4.2 Contraception guidance

Trial subjects must meet the "Reproductive status" inclusion criteria, including contraception requirements, as listed in Section 5.1.

The investigator or delegate should advise the subject how to achieve highly effective contraception. The following birth control methods may be considered as highly effective:

- Intrauterine device. *
- Intrauterine hormone-releasing system. *
- Combined estrogen and progestogen-based contraception: established use of oral, intravaginal, or transdermal hormonal methods of contraception.
- Progesterone-based contraception: established use of oral, injected, or implanted hormonal methods of contraception. *
- Sexual abstinence. **

* Contraception methods that in the context of this guidance are considered to have low user dependency.

** In the context of this guidance sexual abstinence is considered a highly effective method only if defined as refraining from heterosexual intercourse during the entire period of risk associated with the trial treatments. The reliability of sexual abstinence needs to be assessed in relation to its maintenance until Visit 5 (Day 50) and the preferred and usual lifestyle of the subject.

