6.1.2. Definitions and derivations

Unscheduled visits

Unscheduled visits will not be included in the summary tables but will be included in the listings.

Variables

Unless otherwise specified, **baseline** is defined as last value prior to first injection of IMP (Dose 1) given in this BNT162-14 trial on Day 1, including unscheduled visits.

Change from baseline will be calculated as follows:

• Change from baseline = post-baseline assessment value – baseline assessment value.

Duration [days] will be calculated as follows:

• Duration [days] = last observation date – first observation date + 1

Time from first injection (Dose 1) to first reaction will be calculated as follows: Time from first injection to first reaction [days] = first reaction date – date of first injection (Dose 1) + 1

Time from first reaction to last reaction will be calculated as follows:

Time from first to last reaction [days] = last reaction date – first reaction date + 1

Days since last injection will be calculated as follows:

Days since last injection = onset date of AE – date of last injection +1

For conversion of days to months or years the following rules will be applied:

- 1 month = 30.25 days
- 1 year = 365.25 days

Study Day and are defined as follows:

- Study day:
 - If study date < date of first injection (Dose 1), then study day = study date date of first injection
 - If study date >= date of first injection (Dose 1), then study day = study date date of first injection + 1

Fold rise will be calculated as follows:

• Fold rise = post-dose value / baseline value

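### For Group B transplant subjects, the contraception, gamete-donation and no-other-IMP-trial obligations end at Day 50, about 42 to 163 days before injection 2, so the protocol requires none of them after the second exposure

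*Protocol*

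**What the plan says.** Five inclusion criteria in Protocol Section 5.1 stop at Visit 5, Day 50:

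- Criterion 14, contraception for women of childbearing potential (WOCBP): "starting at screening and continuously until Visit 5 (Day 50").
- Criterion 5, other trials: "Agree not to enroll in another trial of an IMP, starting after Visit 0 and continuously until Visit 5 (Day 50").
- Criteria 16, 17 and 18, covering egg donation, male contraception and sperm donation, run from after Visit 0 to the same visit.

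The other sections that mention these obligations lead back to this limit. Section 2.3.1 says "the use of one highly effective method of contraception is required in this trial" because human reproductive safety data are limited, and refers to Section 10.4. Section 10.4.2 refers back to Section 5.1, and its note on abstinence says that reliability "needs to be assessed in relation to its maintenance until Visit 5 (Day 50"). Section 10.4.4 on sperm donation also refers back to Section 5.1.

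The dosing regimen in Section 6 differs for Group B transplant subjects: two injections, "with injection 2 administered 3 to 7 months after injection 1 (Day 1"). Table 2, footnote h, confirms that they are not dosed at Visit 3. Footnote m provides for a further consent at Visit 6 or 7, at which these subjects are informed "on Dose 2 and informed consent must be collected". Table 2a then governs their follow-up from Visit 8. It restarts none of the five obligations, and its eligibility row is blank.

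**The concern.** A fixed Day 50 end works for a schedule that finishes dosing on Day 1 (Group A) or about Day 22 (other Group B subjects), because some weeks of cover remain after the last dose. Protocol version 4.0 added a much later second dose for transplant subjects and left the end date where it was. The stated reason for requiring contraception applies to injection 2 as much as to injection 1, yet as written the requirement has ended before injection 2 is given.

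Two things are at stake. The first is subject protection: no contraception and no bar on egg or sperm donation is required around or after the second exposure. The second is interpretation of the Dose 2 data: a subject could enter another trial, most plausibly of a non-vaccine product, and that product could affect the safety or titer results. The second effect is possible rather than certain, and it concerns a descriptive cohort.

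**Working it through.** The protocol states no figure for this gap, so there is none to reproduce. The check is date arithmetic.

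**Inputs**

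- End of obligations: Visit 5, Day 50, window ±7 days, so Day 43 to Day 57 (Protocol 5.1; Table 2).
- Injection 2, transplant subjects: 3 to 7 months after injection 1 on Day 1 (Protocol 6; Table 2a).
- Month length: "1 month = 30.25 days" (SAP 6.1.2).
- Injection 2, other Group B subjects: Visit 3, Day 22 (Table 2). Group A has one injection, on Day 1 (Table 1).
- Transplant subjects: 15 (Protocol 4.1).

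**Day of injection 2 in transplant subjects** = 1 + months × 30.25

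- Earliest: 1 + 3 × 30.25 = 91.75, about Day 92.
- Latest: 1 + 7 × 30.25 = 212.75, about Day 213.

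**Gap from end of obligations to injection 2**

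- Visit 5 on Day 50: 92 − 50 = 42 days to 213 − 50 = 163 days.
- Visit 5 at the edges of its window: 92 − 57 = 35 days to 213 − 43 = 170 days.

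**Other month lengths, Visit 5 on Day 50** (Day 50 is 49 days after injection 1, so gap = months × length − 49)

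| Month length | 3 months | 7 months |
|---|---|---|
| 28 d | 35 d | 147 d |
| 30 d | 41 d | 161 d |
| 30.25 d (SAP) | 42 d | 163 d |
| 30.44 d | 42 d | 164 d |

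Every case gives a positive gap.

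**Scheduled cover after the last injection**

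| Group | Last injection | Cover to Day 50 |
|---|---|---|
| A | Day 1 | 50 − 1 = 49 d |
| B, non-transplant | Day 22 | 50 − 22 = 28 d |
| B, transplant | Day 92 to 213 | 0 d |

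**Number affected.** Criterion 5 applies to all transplant subjects, so at most 15. The contraception criteria apply only to WOCBP and to men with WOCBP partners, and the donation criteria to WOCBP and men. Those counts are not given, so the range for the reproductive criteria is 0 to 15.

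**Cover under the proposed end point.** Visit 10 is Day 29±7 after Dose 2: 29 − 1 = 28 days after injection 2, or 21 to 35 days across the window.

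**The case against.** Several points can fairly be made on the other side.

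*The Dose 2 consent may already impose these obligations.* Entry criteria do not bind subjects who are already enrolled, so any duty around injection 2 would work through that consent, which was not available for review. This stands as a limit: what is shown is that the protocol does not require these obligations, not that subjects were never asked to meet them. The protocol should still match whatever the consent says.

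*Some wording could be read as trial-long.* Criteria 14, 16 and 17 refer to the duration of the trial, Section 2.3.1 speaks of the trial as a whole, and Section 10.4.2 ties abstinence to the whole period of treatment risk. But each of these either carries the explicit Day 50 end or refers to text that does. The wording suggests an oversight; it does not close the gap.

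*The comparison with other Group B subjects depends on their being dosed on time.* Section 7.1.2 suggests limits for delaying injection 2 of 3, 5 or 12 weeks. From Day 22 that gives Day 43, 57 or 106, leaving 7 days of cover or none against a fixed Day 50. This is correct, but such delays are contingent, and Table 2 labels Visit 5 as about 28 days after injection 2. The transplant gap is built into the schedule.

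*The 42 to 163 days are not themselves the exposure.* Agreed. The contrast that matters is 0 days of cover after the last dose against 28 or 49. The gap only shows that no visit window can rescue the rule.

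*Other safeguards remain.* There is a pre-dose pregnancy test at Visit 8, pregnancy is a reason to stop dosing (Section 7.1.1), and pregnancies are recorded to the end of the study. Section 6.5 limits live vaccines within 30 days of an injection and adds "Trial subjects should not receive any other vaccines within 14 d before or after any trial injection". A non-trial SARS-CoV-2 vaccination is a listed reason for discontinuing a transplant subject (Section 7.2), and data collected after one are excluded (SAP 6.1). These reduce the risk. None of them requires contraception after injection 2, bars donation or bars entry to a trial of a non-vaccine product.

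*The reproductive risk is modest.* These subjects receive only Comirnaty, and Section 2.3.1 does not suspect teratogenicity. That bears on severity. It does not explain dropping, for one cohort, a measure that the same section requires.

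**Conclusion.** The concern holds. As written, the protocol requires no contraception, no restraint on egg or sperm donation and no bar on joining another IMP trial after the second injection in transplant subjects. Scheduled cover after the last dose is 0 days, against 49 days in Group A and 28 days in other Group B subjects. The obligations end about 42 to 163 days before injection 2, or 35 to 170 days allowing for the Visit 5 window. At most 15 subjects are affected.

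This rests on the SAP month length, though no month length tried changes the conclusion, and on reading the explicit Day 50 end as governing over the more general wording about the trial. It does not extend to the unseen Dose 2 consent. The likeliest explanation is that the Day 50 rule was not adapted when the later dose was added. It should be corrected, mainly to protect subjects; the effect on the Dose 2 data is secondary and uncertain.

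**What to change.** For transplant subjects who receive injection 2, apply the obligations of criteria 5, 14 and 16 to 18 from the Dose 2 consent (Visit 6 or 7) until Visit 10. This gives about the same 28 days as other Group B subjects are scheduled to have. State it in Sections 5.1 and 10.4.2, and make agreement a condition of receiving injection 2. Put the same text in the Dose 2 consent, or confirm that it is already there.

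Two additions are optional. One is a check of contraception over the 14 days before injection 2, modeled on criterion 15: consent at Visit 7 can be as late as Day 202, only 213 − 202 = 11 days before the latest injection date, so consent alone guarantees no minimum period beforehand. The other is to tie the end of the obligations to the last injection throughout Group B, which would also cover delayed second doses in non-transplant subjects.

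The cost is a few lines in the protocol and one paragraph in a consent that is already mandatory, with no added visits or tests. The amendment needs ethics committee approval under Section 10.1.1, and anyone who has already consented to Dose 2 would need to be re-consented if the text is not already in that form.
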